6.1. Assessments

6.1.1. Clinical Asthma Exacerbation

The diagnosis of CAE will be determined by the investigator using the definitions shown below, which are based on the official American Thoracic Society/European Respiratory Society statement (Reddel et al 2009).

In this study, "CAE" is an occurrence of either "severe CAE" or "moderate CAE."

- Severe CAE is defined as a CAE that involves worsening asthma such that
 - the treating physician elects to administer prednisone (or equivalent glucocorticoid treatment) at least 10 mg prednisone equivalent above baseline (Table 4), for at least 3 days

AND

- an unscheduled provider visit such as an office visit, urgent care visit, emergency care visit, or hospitalization
- Moderate CAE is defined as a CAE that involves worsening asthma such that
 - the treating physician elects to administer prednisone (or equivalent glucocorticoid treatment) at least 10 mg prednisone equivalent above baseline (Table 4), for at least 3 days

OR

 an unscheduled provider visit such as an office visit, urgent care visit, emergency care visit, or hospitalization associated with an increase in asthma therapy that does not qualify for "severe CAE" as defined above

Glucocorticoid Treatment	Dose (mg) Equivalent to 10 mg of Prednisone	Comment
Cortisone	50	Includes parenteral
Hydrocortisone	40	Cortisol
Prednisolone	10	-
Methylprednisolone	8	Medrol: includes parenteral SOLU-MEDROL [®]
Triamcinolone	8	-
Betamethasone	0.4	-
Dexamethasone	0.4	Oral or parenteral DECADRON®

 Table 4:
 Systemic Glucocorticoid Treatment Equivalent to 10 mg of Prednisone

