1. STUDY OBJECTIVES AND ENDPOINTS

1.1. Objectives and Endpoints

The objectives of this study are to explore the pattern and amount of albuterol use (as captured in the ABS eMDPI), alone or in combination with other study data, preceding a clinical asthma exacerbation (CAE) and in particular, a severe CAE (as diagnosed by the investigators per the protocol). The hypothesis is that albuterol use will increase several days prior to a severe CAE and can serve as a marker of asthma deterioration.

The endpoints of the trial are the primary outcome measure (ie, CAE/severe CAE) and the primary outcome predictor (ie, albuterol use) alone or in combination with secondary predictors (ie, other study data). Multiple correlates of CAE/severe CAE focused on albuterol use, alone or in combination with other study data, will be modeled to determine which patterns best predict the subsequent development of CAE/severe CAE.

For albuterol use, parameters of interest will include (1) the total number of inhalations in the days preceding the peak of a severe CAE, (2) the number of days prior to the peak of a severe CAE when albuterol use increased, and (3) the number of albuterol uses in the day preceding a severe CAE. Therefore, endpoints are not designated as either primary or secondary.

In addition to albuterol use, inspiratory flow values (maximal inhalational flow [MIF], inhalational volume, inhalation duration, and time to MIF), sleep disruption index (SDI), total daily steps (TDS), and baseline information regarding disease state and demographics will be studied. These data will be analyzed using both a univariate and multivariate approach to determine which patterns best predict the subsequent development of a moderate CAE or severe CAE. Inspiratory flow values are obtained from the eMDPI, SDI is obtained for a subset of patients who agree to participate at specific sites (n=100) from an accelerometer worn on the wrist, and TDS is obtained for a subset of patients who agree to participate at specific sites (n=100) from an accelerometer worn on the ankle. Baseline disease state and demographic information will be obtained at screening.

An additional objective for this study is to evaluate the safety of ABS eMDPI use in patients with exacerbation-prone asthma.

The safety endpoints for this study include:

- adverse event data and
- physical examinations

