2.3. Sample Size and Power Considerations

Assuming an expected dropout rate of 10%, it is recommended that 400 patients be enrolled so that 360 evaluable patients complete the study. The rationale is based on a review of the relevant literature, as follows.

Based on previous studies of a poorly-controlled exacerbating asthma cohort ([Bateman et al 2015](#), [Ko et al 2012](#), [McCarren et al 1998](#), [Quezada et al 2016](#)), it is expected that between 20% and 25% of subjects at risk in this patient population will experience a CAE (event) over 3 months, resulting in 72 to 90 expected CAE events in this study. In addition, it is expected that approximately 6.7% and 15% ([Bousquet et al 2007](#), [Ko et al 2012](#), [Kuna et al 2007](#), and [Rabe et al 2006](#)) of subjects at risk in this patient population will experience moderate and severe events, respectively, resulting in approximately 78 events (24 moderate events and 54 severe events) in this study.

This sample size (n=400 patients; 72 to 90 CAE events) is considered adequate for fulfillment of the study objectives using univariate and multivariate analyses to evaluate the relationship of the pattern of albuterol use, inspiratory flow, SDI, and TDS data associated with the subsequent development of a moderate CAE or severe CAE. Per the study by Patel ([Patel et al 2013](#)), a statistically significant relationship was established between prior mean daily SABA usage at baseline and subsequent CAE, studying 45 exacerbations ($p < 0.006$).

In the present study, approximately 72 to 90 CAE events are desired for this trial because the model's fitting of the current study involves the analysis of multiple predictors as described in more detail below.

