7.1.2. Analysis Methods for Albuterol Use

7.1.2.1. Pattern of Baseline Daily and Weekly Albuterol Use

Summary statistics including 95% CIs of the proportion of eMDPI time on study days when a patient took 0 to 4 inhalations a day (number of days a given patient took 0 to 4 inhalations a day divided by the total number of eMDPI study days for a given patient) will be summarized overall and by CAE status and by CAE severity. In addition, the proportion of patients exhibiting

weekly baseline albuterol use (Week 1, Week 2, ..., Week 12) will be summarized overall and by CAE status and by CAE severity.

Week 1 and Week 2 patient albuterol use patterns, “WK1:I#iD#dMT4Y/N” and “WK2:I#iD#dMT4Y/N” designation, will be summarized descriptively (counts and percent) overall and by CAE status and by CAE severity.

7.1.2.2. Total Number of Inhalations in the Days Preceding the Peak of a CAE

For patients who experienced a CAE, summary descriptive statistics of the total number of inhalations taken in 1 day (eg, the 24-hour period on the day prior to the date of the CAE symptom peak) and at 3, 5, 7, 10, 14, and 21 days preceding the date of the CAE symptom peak will be presented overall and by moderate CAEs and severe CAEs.

In this analysis, among patients experiencing more than 1 CAE, the subsequent CAEs can be considered a separate CAE distinct from the first (preceding) CAE provided the patient exhibited at least 1 day of baseline albuterol use after the first (preceding) CAE’s date of symptom peak and prior to the subsequent CAE’s date of symptom peak. For patients who experience multiple CAEs (eg, 3), for a given number of days preceding a CAE (eg, 21 days), if the (eg, third) CAE overlaps with the time period of the preceding (eg, second) CAE, the CAE (eg, third CAE) should not be included in the analysis.

Mean and 95% CI of the total number of inhalations per day for each eMDPI study day will be summarized graphically. The number of patients contributing to the summary statistic at study at Day 7, 14, 21, 28, 35, 42, 49, 56, 63, 70, 77, and 84 will also be presented. Three line graphs will be presented in 1 figure: “Overall” and by “CAE Status” (Yes, No). Three line graphs will be presented in a second figure; “CAE Status No”, “CAE Status Yes: Severe” and “CAE Status Yes: Moderate”.

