7.1.2.3. Hypothesis: Albuterol Use Will Increase Several Days Prior to a CAE

The hypothesis under consideration is that albuterol use will increase several days prior to a CAE. Several days will be defined as 7 days prior to the date of the CAE symptom peak for this analysis.

For each subject that experiences at least 1 CAE, Y_1, \dots, Y_7 will represent the number of puffs of albuterol during the 7 days preceding the date of the CAE symptom peak and let Y_8, \dots, Y_{14} will represent the number of puffs taken each day during day 8 through 14 preceding the date of the CAE symptom peak. Under the hypothesis of no increased albuterol use preceding an exacerbation (ie, null hypothesis) assume for subject “xxx” that $Y_i \stackrel{iid}{\sim} Poisson(\lambda_{xxx})$ for all subjects i . Alternatively, if albuterol use does increase prior to an exacerbation, then

$Y_i \stackrel{iid}{\sim} \text{Poisson}(\lambda_{xxx})$ during day 8 through 14 preceding the date of the CAE symptom peak and $Y_i \stackrel{iid}{\sim} \text{Poisson}(\lambda_{xxx} + \delta)$ for the immediate 7 days preceding the CAE(s). Also, for random subject effect, assume λ_{xxx} follows some distribution to account for subject to subject variability. Let d_{xxx} will equal to the mean number of puffs during the 7 days immediately preceding the date of the CAE symptom peak minus mean number of puffs during days 8 through 14 preceding the date of the CAE symptom peak. To assess if albuterol usage increases 7 days prior to a CAE, $H_0: \mu_D = 0$, $H_1: \mu_D > 0$ will be tested using a t-test at the 0.05 significance level.

7.1.2.4. Number of Days Prior to the Peak of a CAE When Albuterol Use Increased

Among patients who experienced a CAE, summary statistics of the number of days prior to the peak of a CAE when albuterol use increased will be presented overall and by moderate CAEs and severe CAEs for 3 thresholds defining an increase in albuterol use;

- (i) First occurrence of a single day's albuterol use exceeding 4 inhalations;
- (ii) First occurrence of a single day's albuterol use exceeding 12 inhalations;
- (iii) First occurrence of a single day's albuterol use exceeding 20 inhalations.

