7.5. Clinical Asthma Exacerbation

7.5.1. Clinical Asthma Exacerbation Definition

A CAE is the primary outcome measure of this study. In this study, a CAE is an occurrence of either a "severe CAE" or a "moderate CAE." defined as the following:

- A severe CAE is defined as a CAE that involves worsening asthma such that
 - the treating physician elects to administer prednisone (or equivalent glucocorticoid treatment) at least 10 mg prednisone equivalent above baseline (Table 2), for at least 3 daysAND
 - an unscheduled provider visit such as an office visit, urgent care visit, emergency care visit, or hospitalization
- A moderate CAE is defined as a CAE that involves worsening asthma such that
 - the treating physician elects to administer prednisone (or equivalent glucocorticoid treatment) at least 10 mg prednisone equivalent above baseline (Table 2), for at least 3 days

OR

- an unscheduled provider visit such as an office visit, urgent care visit, emergency care visit, or hospitalization associated with an increase in asthma therapy that does not qualify for “severe CAE” as defined above

Table 2: Systemic Glucocorticoid Treatment Equivalent to 10 mg of Prednisone

Glucocorticoid Treatment	Dose (mg) Equivalent to 10 mg of Prednisone	Comment
Cortisone	50	Includes parenteral
Hydrocortisone	40	Cortisol
Prednisolone	10	-
Methylprednisolone	8	Medrol: includes parenteral SOLU-MEDROL®
Triamcinolone	8	-
Betamethasone	0.4	-
Dexamethasone	0.4	Oral or parenteral DECADRON®

The designation of a CAE as moderate or severe is denoted by the response to the CRF question “Severity” on the Clinical Asthma Exacerbation CRF page regardless of whether the following CRF questions are answered in the negative or missing:

- “The treating physician elects to administer prednisone (or equivalent glucocorticoid treatment) at least 10 mg prednisone equivalent above baseline, for at least 3 days”
- An unscheduled provider visit such as an office visit, urgent care visit, emergency care visit, or hospitalization

A patient may experience more than 1 CAE during the study period.

Clinical Asthma Exacerbation Status: Clinical asthma exacerbation status is an indicator of whether or not a patient experienced a CAE during study follow-up (Yes, No).

Clinical Asthma Exacerbation Rate: The percentage of patients who experience at least 1 moderate or severe CAE at the end of study follow-up.

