7.5.2.1. Within Patient CAE Analyses

For each CAE event occurring at least 2 weeks after baseline, device-use measures (albuterol use, inhalational flow [MIF], inhalational volume, and time to MIF) will be summarized for each of 2 weeks of interest: first- 'CAE-adjacent week', the week immediately preceding the onset of CAE symptom (ie, day 1 through 7 preceding the date of the CAE symptom onset), and second – 'CAE-Prior Adjacent week', the week preceding that week (ie, during day 8 through 14 preceding the date of the CAE symptom onset). Summary measures of daily and or weekly use will be compared between the two weeks, as proposed below:

Albuterol use measures:

- total number of inhalations in that week
- the maximal daily number of inhalations in that week
- the mean number of daily inhalations (ie, total number of inhalations divided by number of days with number>0)
- occurrence of a single day's albuterol use exceeding 4 inhalations;
- occurrence of a single day's albuterol use exceeding 8 inhalations
- occurrence of a single day's albuterol use exceeding 12 inhalations
- number of days when albuterol use exceeding 4 inhalations;
- number of days when albuterol use exceeding 8 inhalations
- number of days when albuterol use exceeding 12 inhalations

To note, in this analysis, no inhalation in any day will be taken as a 0 count.

Inhalation flow values parameters:

- maximal daily MIF during the week
- minimal daily time to MIF within a week
- maximal total daily inhalational volume within a week,

To note, if no inhalation was taken at a specific day, flow value parameters will be missing and will not be imputed.

Analysis will be based on all patients CAEs for which there are 14 days (or more) prior to the CAE onset, where patient has been on study and CAE free.

Descriptive statistics of use measures in the 'CAE-adjacent week' and 'CAE-Prior Adjacent week' will be presented.

Continuous measures will be compared between the 2 weeks using paired t-test (and Wilcoxon Signed Ranks test) whereas binary patterns will be compared using Mc-Nemar test.

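### SAP 7.5.1 grades exacerbations by the CRF 'Severity' answer even when the recorded criteria fail the severe definition, so the descriptive severe-CAE summaries may include events that do not qualify

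*SAP*

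**What the plan says.** Protocol 6.1.1 gives the diagnosis to the investigator but ties it to written criteria: "The diagnosis of CAE will be determined by the investigator using the definitions shown below". Severe CAE needs both a steroid course (at least 10 mg prednisone equivalent above baseline for at least 3 days) and an unscheduled provider visit. Moderate CAE needs either the steroid course, or an unscheduled visit with an increase in asthma therapy that does not qualify as severe. SAP 7.5.1 repeats both definitions and calls CAE the primary outcome measure.

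The same SAP section then says that moderate or severe is whatever was entered under 'Severity' on the exacerbation CRF page, "regardless of whether the following CRF questions are answered in the negative or missing". The two questions listed after that clause are the steroid course and the unscheduled visit.

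SAP 1.1 states the study's interest as albuterol use "preceding a clinical asthma exacerbation (CAE) and in particular, a severe CAE (as diagnosed by the investigators per the protocol". SAP 8 plans no sensitivity analysis. SAP 20 lists changes to three analysis sets and to the predictive modelling, but does not mention this grading rule.

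**The concern.** A rule limited to missing answers would be an ordinary fallback. This one also covers a recorded No. An event marked severe with No to steroids or No to a visit is analysed as severe although it fails the definition printed just above the rule. An event answered No to both meets neither definition, yet nothing says whether it still counts as a CAE.

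Severe CAE is the outcome of particular interest, and the albuterol-use parameters that SAP 1.1 lists are framed around it. They are reported by severity in 7.1.2.2 (inhalations in the days "preceding the date of the CAE symptom peak will be presented overall and by moderate CAEs and severe CAEs") and in 7.1.2.4 (days before the peak "when albuterol use increased will be presented overall and by moderate CAEs and severe CAEs for 3 thresholds"). If the severe column mixes qualifying and non-qualifying events, its description of pre-exacerbation albuterol use is not a description of the defined outcome. No planned table would show how far that matters.

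**Working it through.** **1. The combinations.** Two Yes/No questions and two grades give 2 × 2 × 2 = 8 fully answered combinations.

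| CRF grade | Steroid | Visit | Against the 7.5.1 definitions |
|---|---|---|---|
| Severe | Yes | Yes | Consistent |
| Severe | Yes | No | Conflict |
| Severe | No | Yes | Conflict |
| Severe | No | No | Conflict; meets neither definition |
| Moderate | Yes | No | Consistent |
| Moderate | No | Yes | Consistent if asthma therapy was increased |
| Moderate | No | No | Conflict; meets neither definition |
| Moderate | Yes | Yes | Ambiguous |

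Four conflict. The last row meets the severe definition, but it also literally meets the steroid limb of the moderate one, because the wording that excludes severe events sits on the visit limb. It has no negative or missing answer, so the quoted clause does not reach it. A missing answer leaves the definition unverified; it does not contradict it. The table counts what the rule permits, not events expected.

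**2. Where the grade is used.** Ten subsections of SAP section 7 split results by severity: 7.1.2.1, 7.1.2.2, 7.1.2.4, 7.1.2.5, 7.2.2.1, 7.2.2.2, 7.3.2.1, 7.3.2.2, 7.4.2.1 and 7.4.2.2. Sections 5.10, 10.2 and 10.3 do so too. All of these outputs are descriptive.

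The pooled analyses do not use the grade. The t-test in 7.1.2.3 is built "For each subject that experiences at least 1 CAE". For the paired comparisons in 7.5.2.1, "Analysis will be based on all patients CAEs for which there are 14 days (or more) prior to the CAE onset". The Kaplan-Meier plot in 7.5.2.2 and the proportions in 7.5.2.4 also take any CAE. Misgrading alone leaves all four unchanged. They move only if both-No events are counted as CAEs.

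**3. The planning figure.** SAP 2.3 expects 360 evaluable patients (400 × 0.90) and rates of 6.7% moderate and 15% severe, "resulting in approximately 78 events (24 moderate events and 54 severe events) in this study". Check: 360 × 0.067 = 24.1, 360 × 0.15 = 54.0, sum 78.1. The figure reproduces and is not in dispute.

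**4. Illustration.** The documents give no discordance rate. Assume that a fraction f of the 54 severe-labelled events has a No on at least one criterion. The number failing the definition is 54f.

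| f (assumed) | Fail the severe definition | Severe left | Moderate, if all meet a moderate limb | Total CAEs, if none does |
|---|---|---|---|---|
| 5% | 2.7 | 51.3 | 26.7 | 75.3 |
| 10% | 5.4 | 48.6 | 29.4 | 72.6 |
| 20% | 10.8 | 43.2 | 34.8 | 67.2 |

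The last two columns are 24 + 54f and 78 − 54f. They are the two extremes. An event with only a visit belongs under moderate only if therapy was also increased, so having exactly one Yes does not settle the category.

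**The case against.** The best defence is that both documents make the investigator the diagnostician, so the 'Severity' field is the natural source and two tick-boxes need not be more accurate. The exacerbation visit can coincide with the unscheduled visit (protocol 7.1.1), so an answer might be given before the steroid course is complete. This stands as a reason not to replace the investigator's grade as the main grade. It does not remove the conflict, because the investigator is told to use the definitions.

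A second defence is that existing safeguards may leave few discordant events: source documents (protocol 7.1.1), logical checks and queries (protocol Appendix H), and pre-lock review of violations of primary outcome measure criteria (SAP 5.9). That is fair, and the edit-check specifications are not among the documents. But no section names a check of 'Severity' against its criteria. For an event still discordant after query, the only instruction is 7.5.1, which lets the label stand.

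Third, the SAP introduction says the SAP prevails over the protocol. That does not help when the definition and the override both sit in SAP 7.5.1. The introduction also requires differences to be explained in the SAP or the clinical study report (CSR). The SAP does not explain this one; the CSR still could.

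Fourth, the by-patient listings in section 7 might show the discordance. Their columns are not specified, so this is possible but not assured.

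A reader might infer more than the text supports: that the tests in 7.1.2.3 and 7.5.2.1 are compromised, or that the sample size is wrong. The tests pool severities, and the planned event counts do not depend on the rule. Nor do the documents show that any discordant event exists.

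**Conclusion.** The inconsistency is real and should be repaired. SAP 7.5.1 holds a definition and a grading rule that disagree in four of eight fully answered combinations. Followed as written, the rule puts any event labelled severe that fails the joint criteria into the severe column.

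The consequence is bounded. It falls directly on descriptive severity splits, most importantly 7.1.2.2 and 7.1.2.4. It reaches 7.1.2.3, 7.5.2.1, 7.5.2.2 and 7.5.2.4 only if events meeting neither definition are counted. Its size is unknown: the 5% to 20% range is an assumption without a source in the documents, and it considers only events labelled too high. No error in sample size, power or significance level follows.

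**What to change.** 1. Before database lock, query every record whose 'Severity' disagrees with the two criteria, using the process in protocol Appendix H.
2. Tabulate investigator severity against the steroid and visit answers, including missing ones.
3. Keep the investigator's grade as the main grade unless the sponsor prefers otherwise. Repeat the severity summaries in 7.1.2.2 and 7.1.2.4 under a definition-based grade:
   - both Yes is severe;
   - steroid only, or visit only with a recorded increase in asthma therapy, is moderate;
   - visit only with no recorded increase is flagged as unverified, not excluded, because the medication inquiry in protocol 5.6 covers medications other than the study inhaler;
   - where an answer is still missing, use the investigator's grade.
4. List both-No events. Show 7.1.2.3, 7.5.2.1, 7.5.2.2 and 7.5.2.4 with all investigator-reported CAEs (main) and without both-No events (sensitivity).
5. Amend SAP 8 to include these analyses, and explain the grading rule in SAP 20 or the CSR.

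The cost is one derivation from questions already on the CRF page, one cross-table, one listing, two repeated descriptive summaries, four pooled results shown a second way, and short text edits. The CRF is not among the documents, so the programming effort is an estimate, as is whether the increase in therapy can be read from the same page. The severe count may be slightly smaller under the definition. If there is no discordance, the cross-table shows it and the repeated summaries will match except for any visit-only events flagged as unverified.
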